The inconsistent cross-sectional case-control and prospective findings between body composition and fat oxidation could partly be due to numerous methodological discrepancies between studies such as participant characteristics, matching of comparative groups, the exercise protocol utilised and / or the assessment of body composition, lipid oxidation and cardio-respiratory fitness levels. For example, two recent studies suggest that adiposity may not influence fuel use independently of cardiorespiratory fitness in recreationally active males [34] and females [33], albeit limited by small sample sizes ($n = 24$ and 14 , respectively) and the restricted adiposity range evident (normal and overweight range) [33]. Moreover, adipose tissue distribution, not total levels per se, may independently be associated with substrate metabolism during exercise [32, 48, 49]. Peak fat use during exercise was reportedly lower in females with higher abdominal to lower body fat mass distribution compared to low abdominal: lower body fat mass ratio [48, 49]. However, the females recruited were all categorised as being of 'normal' weight. To our knowledge, no comprehensive data exists on exploring the relationships between body composition (total and distribution of body fat), muscle and adipose tissue function, and whole-body fat oxidation in both post-absorptive resting and exercising conditions, and thus, should be further explored.

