Lastly, this study will also address the intra-individual variability and reliability of fat oxidation at rest and during exercise by asking individuals to complete two identical main trial days 7 – 14 days apart. Intra-individual variability has become a recent topic of great interest in metabolism research [59-61]. The few studies to date that have investigated the intra-individual variability of fat use during exercise are not only confounded by the above recruitment issues, but have also not reported data on an individual level or systematically applied the wide range of reliability statistical methods available [15, 62-68]. Intra-individual variability may partially account for the previously reported inter-individual variability in fat use and thus, only once accounted for can determinants of fat use be more precisely determined. Importantly, this has not previously been considered in determinant studies. Thus, we will apply the entire range of reliability statistical methods available to assess intra-individual variability and when reporting the results of the current study, will plot anonymous individual data alongside group means. This will provide a highly systematic and valid evaluation of the reliability and intra-individual variability of fat use at rest and during exercise alongside drawing firmer conclusions on potential determinants.

Overall, this project will extensively explore fat oxidation in a wide range of ‘healthy’ and ‘at risk of metabolic disease’ adults under two proposed metabolic flexibility paradigms; post-absorptive resting and exercising conditions. This will provide important insights into fat use at rest and during exercise, help evaluate current and future research, and aide in the design of future nutrition and exercise interventions to improve human health.

Study Aims / Objectives:

Therefore, the objectives of this study are to comprehensively and systematically explore whether whole-body fat use at rest and during exercise is:

- 1) Altered in individuals with overweight or obesity compared to lean individuals
- 2) Associated with a wide range of physiological, metabolic, lifestyle and genetic variables (i.e. potential determinants or health outcomes)
- 3) The true inter- and intra-individual variation in fat use which will help to more confidently determine the above objectives.

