A sample size estimation of 200 participants was determined via two methods. Firstly, R² values (36% and 13%) from two stepwise multiple linear regression models predicting the variance of peak fat use during exercise (g/min and mg/kg Fat Free Mass/min, respectively) in 300 healthy male and female adults were used [54]. Using these R² values, 42 and 119 participants were required, respectively, to provide a 95% chance of detecting this variation in PFO with α set at 0.05. Secondly, Cohen [76] defines the above effect sizes as large and

medium, respectively. A sample size estimation chart produced by Miles and Shevlin [77] with ten predictors was consulted as a guide. Conservatively, to detect a medium effect size with a power of >95%, approximately 180-190 participants would be required. Taking into account the above, a sample of two-hundred participants was decided upon to account for rolling recruitment, loss of follow-up data due to study withdrawal, non-completers, replacement of drop-outs and any unforeseen issues in data collection.

To minimise the negative impact of loss of follow-up data to validity, participants will be provided with a detailed participant information sheet and have the experimental protocol explained verbally before the onset of the study. They will be advised to carefully consider the required time investment and effort required to complete the study. As such, we hope that exclusions based on likely withdrawals can be accounted for prior to participation. Any unforeseen change in circumstance or withdrawal of consent resulting in loss of follow-up data will be fully documented in the final trial report.

Statistical / Data Analysis

Primary Outcome Measure:	Maximal rate of whole-body fat oxidation (mg/kg FFM/min)
Secondary Outcome Measures:	Maximal rate of whole-body fat oxidation (g/min)
	FAT _{MAX} (% of maximum oxygen consumption)
	FAT _{MAX} (% of Watt max)
	FAT _{MAX} (% of Heart Rate max)
	Resting rate of whole-body fat oxidation (mg/kg FFM/min)
	Resting rate of whole-body fat oxidation (g/min)
	Resting Metabolic Rate (kcal/min)
	$\dot{V}O_{2peak}$
	Habitual Energy Intake (kcal/day)
	Habitual Macronutrient Intake (grams per day)
	Habitual Physical Activity Energy Expenditure (kcal/day)

	Menstrual Cycle (Self-reported and sex hormone concentrations in blood [Estrogen and Progesterone])
	Fasting measures of blood metabolites: Glucose, Triglycerides, Cholesterol, NEFA, glycerol

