	Fasting measures of Adipokines: Leptin, Adiponectin
	Fasting measures of Catecholamines: epinephrine and norepinephrine
	Fasting measures of sex hormones: 17 beta-estradiol, testosterone, progesterone
	Fasting pancreatic derived hormone concentrations: insulin and glucagon
	Hydration Status: Urine Specific Gravity
	Age (years)
	Sex
	Ethnicity
	Smoking Status
	Medication / Supplement Use
	Dietary Patterns / Requirements
	Body Fat Percentage
	Lean Body Mass (kg)
	Body Fat Distribution
	Waist and Hip Circumference
	Fat Mass Index
	Genotype analysis
	Skeletal Muscle Characteristics (Protein Content and / or Activity)
	Adipose Tissue Characteristics (Protein Content and / or Activity)

Data will be checked for normal distribution prior to analysis via Shapiro-Wilk's normality test and visual inspection of histograms. Parametric tests will be conducted on normally distributed data. Non-normally distributed data will be log-transformed if appropriate or the equivalent

non-parametric tests will be conducted. Statistical significance will be set at $P < 0.05$. The statistical analysis for the study objectives identified above are as follows:

- 1) The effect of body composition on whole-body fat use will be tested by separating groups into defined categories (e.g. lean, overweight or obese) and conducting a one-way ANOVA and mixed design model. The latter to test for any interaction effects across the two main trial days.
- 2) To identify determinants / characteristics that may be associated with whole-body fat use, correlation analysis will firstly be conducted between whole-body fat use at rest and during exercise with each variable. Statistically significant correlates will then be added to a follow-up hierarchical regression analysis to predict whole-body fat use at rest and during exercise.
- 3) At a group level, intra-individual variation in whole-body fat use will be tested by a paired sample t-test. A range of further reliability / variability tests will be conducted to comprehensively determine intra-individual variation: Pearson correlation coefficient, Intra Class Correlation, Coefficient of Variation, Bland-Altman plots with 95% Limits of Agreement and Typical Error. Additionally, individual data will be plotted on graphs alongside group means.

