- 4) The inter-individual variation in fat use will be determined by observing the range of whole-body fat use estimates at rest and during exercise recorded after controlling for intra-individual variability / calculated measurement error.

Ethical Considerations / Potential Risks and Discomfort

Skeletal muscle and Adipose Tissue Biopsies: The main ethical issues anticipated relate to the relatively invasive optional skeletal muscle and adipose tissue samples to be acquired at Visit 4. However, as noted, both of these biopsies are optional and thus, participants will be freely able to choose whether or not to have these procedures. The skeletal muscle and adipose tissue biopsies will be obtained to look at associations between fat use at visit 2 and 3, and characteristics of these tissues obtained at Visit 4 (e.g. content and activity of proteins involved in substrate metabolism, skeletal muscle fibre composition and mitochondrial content, location and function). Both techniques are well established procedures in Human Physiology research and are regularly performed in the physiology laboratories at the University of Bath. Only

minor complications are typically observed (such as bleeding from the skin wound, bruising and minor soreness over the days afterwards). For example, the minor complication rate was reportedly 0.15% when using the Bergstrom muscle biopsy technique [78]. Participants will be fully explained the risks associated with the procedures and are provided with an extensive guide (included with the participant information sheet) to help manage these issues if opted for. These sheets also list the possible complications which are more severe (e.g. intramuscular bleeding, denervation or infection) although these complications are fortunately very rare and risks are further minimised by following best practice. All procedures will be performed only by trained individuals to minimize any risk and the minimum amount of each tissue will be taken to minimise discomfort whilst gaining the maximum information to answer the research questions.

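### Item 4 of the analysis plan measures inter-individual variation by an observed range and does not specify how intra-individual variability is removed first

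*Combined protocol and SAP*

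**What the plan says.** Objective 3 (Study Aims / Objectives) is "The true inter- and intra-individual variation in fat use which will help to more confidently determine the above objectives". The numbering of the analysis list differs from that of the objectives: items 3 and 4 of Statistical / Data Analysis together serve Objective 3.

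Item 3 deals with the within-person half and names its statistics, among them "Intra Class Correlation, Coefficient of Variation, Bland-Altman plots with 95% Limits of Agreement and Typical Error". Item 4 deals with the between-person half in one sentence: "The inter-individual variation in fat use will be determined by observing the range", which is spelled out as the "range of whole-body fat use estimates at rest and during exercise recorded after controlling for intra-individual variability / calculated measurement error". It gives no model or formula for that control. It does not say whether one visit or the average of two is used, and it plans no interval.

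Item 1 includes a mixed design model, but its stated purpose is different: "The latter to test for any interaction effects across the two main trial days".

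The plan is for 200 participants with two identical main trial days each. It gives no ICC, SD or other reliability figure for fat use.

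**The concern.** The control step is what turns an observed spread into a true one, and it is left open. Common ways of carrying it out err in opposite directions. An average of two visits still carries half the within-person variance, so its range is too wide. Person estimates shrunk towards the group mean vary less than the true person values, so their range is too narrow. Rescaling the estimates so that their variance matches the between-person variance would recover the right range under normality, but it needs the between-person SD first. The same data could therefore give a spread that is too large or too small, depending on a choice that could be made after the results are seen.

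The statistic is also a weak one for this purpose. A range is set by the two most extreme people and widens as more people are analysed, so it would change with dropout alone. It is also less precise than an SD from the same data.

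**Working it through.** The plan has no figure of its own for between-person variation to reproduce. The inputs are n = 200 and two visits (from the plan), between-person SD set to 1 as the unit, normal data, and an ICC of 0.5 to 0.9. The last three are assumptions.

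**1. Dependence on n.** The expected range of n independent normal values, by numerical integration, is 5.02 SD at n = 100, 5.42 at n = 180 and 5.49 at n = 200. In simulation at n = 200, 95% of ranges fell between 4.51 and 6.72 SD, a relative standard error of 10.3%.

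**2. Effect of the control step.** With between-person variance 1, the within-person variance is w = (1 - ICC)/ICC.
- Two-visit means have variance 1 + w/2 = (1 + ICC)/(2 ICC). Their range relative to the true range is sqrt[(1 + ICC)/(2 ICC)].
- Shrinkage multiplies each mean by its reliability, 2 ICC/(1 + ICC). The range relative to the true range becomes sqrt[2 ICC/(1 + ICC)].

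Multiplying by the true expected range of 5.49:

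| Assumed ICC | Two-visit means | Error | Shrunken estimates | Error |
|---|---|---|---|---|
| 0.5 | 6.73 | +23% | 4.48 | -18% |
| 0.6 | 6.34 | +15% | 4.76 | -13% |
| 0.7 | 6.05 | +10% | 4.98 | -9% |
| 0.8 | 5.83 | +6% | 5.18 | -6% |
| 0.9 | 5.64 | +3% | 5.35 | -3% |

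Simulation agrees. These two readings do not bound the problem. At ICC 0.7, the unadjusted single-visit range averages 6.56, the range of two-visit means less twice the typical error 4.73, and the single-visit range less 2 x 1.96 typical errors 3.99.

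**3. Precision of the alternative.** The between-person variance is the variance of the two-visit means minus half the squared typical error, each on 199 degrees of freedom. Its standard error is sqrt{2[(1 + w/2)^2 + (w/2)^2]/199}, and the relative standard error of the SD is about half of that.
- ICC 0.5 (w = 1): sqrt[2(2.25 + 0.25)/199] = 0.159, so about 8%.
- ICC 0.7 (w = 0.429): sqrt[2(1.474 + 0.046)/199] = 0.124, so about 6.2%.
- ICC 0.9 (w = 0.111): sqrt[2(1.114 + 0.003)/199] = 0.106, so about 5.3%.

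Simulation gives 8.0%, 6.2% and 5.3%, with the estimate averaging 0.997 to 0.999 of the true SD.

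**4. The item 3 statistics are enough.** Typical error x sqrt[ICC/(1 - ICC)] equals the between-person SD. At ICC 0.7 the typical error is sqrt(0.429) = 0.655 and sqrt(0.7/0.3) = 1.528; the product is 1.00. In 15 simulated data sets this formula and a random-intercept model fitted by REML differed by at most 0.00003.

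**5. Without normality.** With skewed or two-group person effects the pattern holds. Two-visit means overstate by 27 to 29% at ICC 0.5 and 4 to 6% at 0.9; shrunken estimates understate by 14 to 16% and 0 to 2%. The relative standard error is 4.7 to 9.8% for the SD against 8.6 to 18% for the range.

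**The case against.** The strongest reply is that little is missing. Item 3 already plans an ICC, which is the between-person share of variance, and a typical error from the same two visits. The calculated measurement error in item 4 plausibly means that typical error, and individual data will be plotted. This stands as a limit on the point: the gap is in specification, not in data. But item 3 assigns those statistics to intra-individual variation, and item 4 then names a range, so the plan itself does not make the connection.

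Second, the size depends on an ICC that the documents do not give. At 0.8 to 0.9 the error is 3 to 6%, less than the range's own 10% standard error; at 0.7 the two are about equal; only at 0.5 to 0.6 is the error clearly larger. The two readings of the control step are also illustrations, not the plan's words. Both remarks are fair. They weaken the size, but not the observation that the wording admits several answers.

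Third, a range is honest description in an exploratory study and needs no distributional assumption. That is true of a description of this sample. Objective 3, however, asks for the true variation, which is more than description.

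**Conclusion.** The point holds as a matter of specification. Item 4 names a statistic that depends on n, rests on two people and is biased under obvious ways of controlling for within-person variation, while a more precise estimate follows from statistics already planned. The bias runs from about 3% either way at an ICC of 0.9 to +23% or -18% at 0.5, under normality, n = 200 and the two readings worked above. The wording gap is certain; its numerical size is not.

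A reader might infer more than the documents support:
- That true between-person variation cannot be estimated under this plan. It can: two visits per person identify it, and the ICC and typical error in item 3 determine it.
- That the range will be set against the smaller studies in the background, "albeit limited by small sample sizes" (24 and 14). Those are cited on adiposity and fuel use, and no such comparison of ranges is proposed.
- That item 3 relies on the paired t-test to measure within-person variation. It uses that test at group level and lists proper measures alongside it.

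The objective is exploratory with no decision rule attached, and neither the sample size nor the primary outcome is affected.

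**What to change.** In item 4, make the between-person SD the estimate of inter-individual variation. Obtain it from a random-intercept model with visit as a fixed effect or, equivalently, as typical error x sqrt[ICC/(1 - ICC)] with a consistency-type ICC and complete pairs. State that this uses the item 3 quantities. Report the SD and the ICC with 95% confidence intervals by a named method, for example profile likelihood or a bootstrap that resamples participants. Work on the log scale where the normality check already planned shows skew. Keep the range as description only, stating n and whether it comes from single visits, two-visit means or model estimates.

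The cost is a few lines of text and one extra model per outcome, with no new data, visits or participants. The downside is that the intervals assume roughly normal person effects, which a descriptive range does not. In simulations with skewness 1, a bootstrap interval for the SD covered about 93% at ICC 0.5 and 90 to 92% at ICC 0.9, instead of 95%. The log scale is the natural remedy, but how far it restores coverage was not checked.
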